1 AMENDMENTS AND UPDATES (PROTOCOL HISTORY)

The protocol version 2, dated 12 November 2014, Appendix A, Appendix B and section 5.7.6 for the Skindex-29 Questionnaire were updated. As these were administrative changes, no amendment was required; only a new protocol version number was issued. The protocol Amendment 1 will originate version 3 to extend ongoing patients and newly enrolled patients for a total of 24 months from consent date. An additional new quality of life assessment has been added.

2 STUDY MILESTONES

This study will be conducted according to the following schedule:

First patient, first visit: Q4 2014

Last patient, first visit: Q3 2017

Last patient, last visit: Q3 2019

3 RATIONALE AND BACKGROUND

Background

Mycosis fungoides cutaneous T-cell lymphoma (MF-CTCL) can present as patches, plaques, or tumors on the skin, often in areas of the body that are not usually exposed to the sun [[Lymphoma.org 2011](#)]. While MF-CTCL is rare, it is the most common type of cutaneous T-cell lymphoma (CTCL), accounting for 50–70% of all CTCLs [[Imam 2013](#)]. It is estimated that approximately 16,000 to 20,000 people in the US have the disease and that the 5-year incidence of MF-CTCL for all stages was 0.56 per 100,000 person-years between 2005–2009 [[Korgavkar 2013](#), [Leukemia & Lymphoma Society 2011](#)]. The prevalence and incidence of MF-CTCL are likely to be under-reported due to nomenclature variances and because the symptoms and skin biopsy findings can appear similar to other types of skin conditions [[Lymphoma.org 2011](#), [Criscione 2007](#)]. Patients frequently present with early stage disease typically associated with a favorable prognosis and survival of 10–35 years, but over 25% progress to advanced disease with a median survival of less than 4 years and just 13 months in those with nodal involvement [[Scarisbrick 2014](#)]. The most important clinical predictive factors for survival include patient age, T classification, and the presence of extracutaneous disease [[Kim 2003a](#)].

Although there is currently no cure for the disease, patients diagnosed at early stages of MF-CTCL (Stages IA, IB, or IIA) and receiving treatment for the disease have a median survival of 35.5, 21.5, and 15.8 years, respectively [[Agar 2010](#)]. Topical mechlorethamine hydrochloride (MCH or nitrogen mustard) has been used to treat

MF-CTCL since the 1950s [Lessin 2013]. The National Comprehensive Cancer Network [NCCN] Guidelines list topical MCH as a primary skin-directed treatment option for patients with MF-CTCL with limited/localized skin involvement or for generalized skin involvement [NCCN 2014]. Topical MCH has been available in aqueous and petrolatum-based forms. However, both forms have disadvantages that limit patient acceptance [Kim 2003b, Ramsay 1995].

Valchlor, approved by the FDA in August 2013 for Stage IA and IB MF-CTCL, is a fast-drying, greaseless gel formulation that has been shown to be effective and safe in a clinical trial [Lessin 2013]. Two hundred sixty (260) patients in the Valchlor clinical trial (Study 201) received MF-CTCL specific treatment up to 12 months [Lessin 2013]. In the open-label, single group extension trial, 98 patients who completed Study 201 without a complete response received treatment with a formulation identical to Valchlor but containing MCH HCl 0.04% for 7 months. Currently, Valchlor is the only FDA-approved formulation of topical MCH, and one of two FDA-approved topical treatments for MF-CTCL [Kim 2014]. The results of the randomized, controlled, multi-center trial confirmed the non-inferiority of Valchlor in the treatment of MF-CTCL when compared to ointment-based MCH.

Rationale

Prospective data on Valchlor are currently only available from the pivotal, randomized, controlled clinical trial with strict inclusion and exclusion criteria. Understanding real-world patient safety and tolerability, as well as compliance and discontinuation rates, will assist with the future management of Valchlor-treated MF-CTCL patients. This study will build and extend on the data from the Valchlor clinical development program, increase the understanding of the use of Valchlor in patients with MF-CTCL and, while limited to patients treated with Valchlor, will represent the largest prospective study with any given MF-CTCL treatment.

This large, non-interventional study will provide information on the use of Valchlor in a 'real-world' clinical practice setting. This study will increase understanding of the management and outcomes of Valchlor-treated MF-CTCL patients by observing clinical characteristics, treatment patterns, outcomes (e.g., clinical status and healthcare utilization [MF-CTCL-related hospitalizations and emergency room visits]), and adverse events (AEs). Additionally, a better understanding of the disease burden of MF-CTCL will be gained by collecting patient-completed symptoms and quality of life (QOL) questionnaires.

4 RESEARCH QUESTION AND OBJECTIVES

The objectives of the MF-CTCL prospective cohort study are:

- To describe clinical characteristics of patients treated with Valchlor at enrollment and during the study observation period.
- To describe treatment and response assessment patterns of patients with MF-CTCL treated with Valchlor at enrollment and during the study observation period.
- To assess outcomes (e.g., clinical status and rates of healthcare utilization [MF-CTCL-related hospitalizations and emergency room visits]) in patients with MF-CTCL treated with Valchlor during the study observation period.
- To collect and describe the incidence of AEs/SAEs in patients with MF-CTCL treated with Valchlor:
 - To estimate the incidence of dermatitis in patients using Valchlor during the study observation period.
 - To describe the management of dermatitis in patients using Valchlor at enrollment and during the study observation period.
- To collect patient-completed symptoms and QOL questionnaires.

5 RESEARCH METHODS

5.1 Study design

This is a multi-center, prospective, observational study of MF-CTCL patients who have newly initiated Valchlor or who are continuing treatment with Valchlor.

Patients will be followed by their physician according to routine clinical practice. With the exception of protocol-required patient-completed questionnaires, there are no specific or mandated clinical assessments to be performed, and patients will not receive experimental intervention or treatment as a consequence of their participation in this study. The study protocol will not mandate any specific schedule of visits. Patients will undergo clinical assessments and receive standard medical care as determined by the patient's physician in a real-world setting.

Patients will be followed prospectively for a maximum of 2 years from the date of signed informed consent until end of study (EOS), which includes withdrawal of consent, loss to follow-up, death, or study completion. Continuation in the study is not contingent on continuation of Valchlor.

The study will end after all enrolled patients have been followed for 2 years, or discontinued from the study for any reason.

5.2 Population (setting and study population)

This study will enroll approximately 300 MF-CTCL patients being treated (newly initiated or continuing treatment) with Valchlor [see Section 5.2.1 for details] from up to 50 participating centers/clinics in university-affiliated or community hospitals.

Patients considered ‘being treated with Valchlor’ is comprised of two distinct groups: 1) Patients newly initiating Valchlor. These are patients who are enrolled at their first office visit after having initiated Valchlor; 2) Patients continuing treatment with Valchlor. Patients must be actively taking Valchlor on the day of enrollment.

All consecutive MF-CTCL patients being treated with Valchlor [see Section 5.2.1 for details] seen at the participating centers are eligible for enrollment in the study, regardless of other MF-CTCL therapies received before or at the time of enrollment.

5.2.1 Inclusion criteria

- All adult patients (≥ 18 years of age) diagnosed with MF-CTCL and being treated with Valchlor. This includes patients newly initiating Valchlor OR patients continuing treatment with Valchlor:
 - Patients newly initiating Valchlor are patients who have their first office visit after having initiated Valchlor.
 - Patients continuing treatment with Valchlor includes patients who are actively taking Valchlor on the day of enrollment.
- Signed patient informed consent.

5.2.2 Exclusion criteria

- None.

5.3 Variables

The variables of interest for this study includes clinical characteristics at enrollment and during the study observation period, treatment patterns, clinical status, as assessed by the physician (including the methods used in practice to assess clinical status), MF-CTCL-related healthcare utilization, as assessed by the physician (hospitalizations and emergency room visits), AEs and SAEs, patient-completed symptoms and QOL questionnaires.

Data elements to be collected from the patient’s medical record at study enrollment and at post-enrollment follow-up visits are shown in [Table 1](#). Additionally, pre-treatment data collection using specific variables will be performed at enrollment. These variables include weight, tumor-node-metastasis-blood (TNMB) classification, use of Valchlor and other MF-CTCL treatments, and clinical status assessments. Drug holidays (temporary discontinuation) from Valchlor will be captured on the electronic Case Report Form (eCRF) by recording start and stop dates of all MF-CTCL treatments. Patient-completed questionnaires will be administered to patients who can read and understand English or Spanish and are able to self-complete the questionnaires based on the investigator’s assessment. Patients who are unable to read and understand English or Spanish will not be asked to complete the questionnaires and will be excluded from the study.

Confidential

Table 1 eCRF Data Collection

| Variables | Enrollment visit | Post-enrollment follow-up visits |
|---|-------------------------|---|
| Informed Consent | X | X ¹ |
| Demographics | | |
| Age, gender, race/ethnicity, height | X | |
| Weight* | X | |
| Relevant Medical History | | |
| Age at diagnosis of MF-CTCL | X | |
| Date of MF-CTCL diagnosis | X | |
| Method of diagnosis | X | |
| MF-CTCL TNMB classification* | X | |
| MF-CTCL TNMB classification change | | X |
| MF-CTCL histology | X | |
| Malignancies and secondary malignancies | X | |
| Non-melanoma skin cancers | X | |
| Prior viral infections | X | |
| Atopic disorders | X | |
| Psoriasis | X | |
| Urticaria | X | |
| Mental disorders | X | |
| Family medical history | X | |
| Other relevant medical history | X | |
| Changes in medical history | | X |
| Targeted MF-CTCL Treatments (Medication Use and Dosing)*[†] | | |
| Valchlor | X | X |
| Other MF-CTCL treatments | X | X |

| Variables | Enrollment visit | Post-enrollment follow-up visits |
|---|------------------|----------------------------------|
| Healthcare utilization related to MF-CTCL (as assessed by physician) | | |
| Hospital admissions [‡] | | X |
| Emergency room visits | | X |
| Clinical Status (as assessed by physician) | X | X |
| Clinical Status Assessments* | | |
| Composite Assessment of Index Lesion Severity | X | X |
| Modified Severity Weighted Assessment Tool | X | X |
| Physician's Global Assessment | X | X |
| Body Surface Area of disease | X | X |
| Patient-Completed Questionnaires[§] | | |
| Visual Analogue Scale for pruritus | X | X |
| Skindex-29 | X | X |
| Mycosis fungoides / Sézary syndrome-type cutaneous T-cell lymphoma | X | X |
| Safety Measures^{**} | | |
| AEs and SAEs | X ⁺ | X |
| Reports of secondary exposures | | X [^] |

*Included in pre-treatment data collection, which is performed at enrollment. All data must be completed as available.

[†]Includes collection of start and stop dates for each medication, including reasons for starting and stopping medications. Start and stop dates are also collected for Valchlor, including short gaps in treatment, such as drug holidays.

[‡]For each hospital admission, length of stay and primary admission and discharge diagnoses will be collected.

[§]To be completed by patients who can read and understand English and are able to self-complete the questionnaires based on the investigator's assessment. Patients who are unable to self-complete the questionnaires will not be excluded from the study.

^{**}Safety measures, which include AEs and SAEs, will be collected from the informed consent date and prospectively at every visit during the study and up to 30-days post-discontinuation of Valchlor during the study. Ongoing AE and SAE data will be collected through the end of study, regardless of Valchlor use.

New AEs and SAEs that occur more than 30 days after discontinuation of Valchlor will be reported to Actelion US Drug Safety if investigator feels there is a possible causal relationship with Valchlor. Investigators are also expected to assess patients for AEs and SAEs and follow the appropriate reporting procedures per Section 7.

⁺All ongoing AEs and SAEs for patients being treated [see Section 5.2.1 for definition of “being treated”] with Valchlor.

[^]All reports of secondary exposures, as available, will be counted on the eCRFs. Additional information regarding secondary exposures will be forwarded directly to Actelion US Drug Safety via the Secondary Exposure Form. Refer to Section 7.1.1 for definition of secondary exposure.

AE = adverse event; eCRF = electronic Case Report Form; MF-CTCL = mycosis fungoides cutaneous T-cell lymphoma; SAE = serious adverse events; TNMB = tumor-node-metastasis-blood.

^lRe-consent at the first follow up visit for subjects who are currently active in the study prior to Amendment 1.

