5.9 Discussion of the study methods (including limitations)

This study is an observational, prospective study examining MF-CTCL patients being treated with Valchlor in a real-world clinical setting. Valchlor treatment will be based on prescriber decision and will not be influenced by participation in this study. The patients will be followed by their physician according to routine clinical practice. The study protocol does not mandate any treatment, procedures or visits. Patient-completed questionnaires, however, are a study requirement and will be administered at all study visits for patients who can read and understand English, and are physically and mentally able to complete the questionnaires based on the investigator's assessment.

Any interpretation of observational study results should consider limitations to observational real-world study designs, including potential sources of selection or information biases, and confounding factors.

To minimize selection bias, participating centers will offer enrollment in the study to all consecutive MF-CTCL patients currently treated with Valchlor [see Section 5.2.1 for inclusion criteria], regardless of other MF-CTCL specific therapy received before or at

the time of enrollment, or during the study. This study collects data on all users of Valchlor. At enrollment, a review of existing medical records will be performed to collect information as described per [Table 1](#) (enrollment visit). Thereafter, all data will be collected during the observation period.

Patients who are enrolled under the original protocol prior to protocol Amendment 1 and are still ongoing in the study will be re-consented under Amendment 1 and will continue to follow the schedule of Table 1 eCRF Data Collection specified in this protocol up to end of study (Month 24). Patients who enrolled and have completed 1 year of the study under the original protocol will not be offered to continue in the study and thus not re-consented under Amendment 1.

To minimize the number of patients lost to follow-up, there will be regular contact with patients by the site, including 3 attempts to contact a patient before she/he is considered lost to follow-up.

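### Protocol Section 5.3 excludes patients who read neither English nor Spanish, while the eligibility section lists no exclusions; the questionnaire language rule also differs between sections.

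*Protocol*

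**What the plan says.** **Who may enter.** Section 5.2.1 of the protocol admits "All adult patients (≥ 18 years of age) diagnosed with MF-CTCL and being treated with Valchlor", subject to signed consent, with no condition on language or literacy. Section 5.2.2 has a single entry, None, and the synopsis agrees. Sections 5.2 and 5.9 and the SAP section on analysis populations make all consecutive treated patients eligible. Section 5.9 adds that the study covers every Valchlor user.

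The text of Section 5.3 departs from this. Patients who cannot read and understand English or Spanish "will not be asked to complete the questionnaires and will be excluded from the study".

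The Table 1 footnote in the same section says: "Patients who are unable to self-complete the questionnaires will not be excluded from the study". The SAP's Table 1 carries the same footnote.

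**Who completes the questionnaires.** Section 5.3 allows English or Spanish. The Table 1 footnote reads "To be completed by patients who can read and understand English and are able to self-complete the questionnaires". Section 5.9 administers them "for patients who can read and understand English, and are physically and mentally able to complete the questionnaires". Neither of these, nor the SAP footnote, mentions Spanish.

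**The concern.** Section 5.3 introduces an eligibility rule outside the eligibility section, and that rule conflicts with the eligibility section. Up to 50 centers work from this protocol. A center that follows Section 5.3 turns away patients whom a center following Section 5.2 enrolls.

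Two things are at stake:

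- **Selection.** Section 5.9 names consecutive enrollment as the means of limiting selection bias. The planned checks compare enrolled patients with and without reported data (protocol Section 5.7.1; SAP, methods for missing data). A patient refused on language is in neither group, so these checks cannot show the loss.
- **Patient-reported data.** The pruritus VAS, Skindex-29 and MF/SS-CTCL instrument are secondary endpoints in the SAP. The SAP imputes nothing and does not expect data to be missing at random. Whether a Spanish-only reader contributes to these endpoints depends on which passage the center followed.

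**Working it through.** This is a conflict of wording, so the main check applies each passage to the same types of patient.

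| Patient | Section 5.2 and synopsis | Section 5.3 text | Table 1 footnote (protocol and SAP) | Section 5.9 |
|---|---|---|---|---|
| Reads English, can self-complete | In | In, asked | In, asked | In, asked |
| Reads Spanish only, otherwise able | In | In, asked | In, not asked | In, not asked |
| Reads neither language | In | **Out** | In, not asked | In, not asked |
| Reads English, cannot self-complete for another reason | In | In, not asked | In, not asked | In, not asked |

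The third row is the eligibility conflict, and Section 5.3 stands alone in it. Its clash with Section 5.2.2 is direct. Its clash with the footnote takes one step of inference: someone who cannot read the form cannot complete it unaided. The second row is the language conflict, in which Section 5.3 is again alone.

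The Section 5.3 sentence is also odd in itself. A patient who is not in the study needs no instruction about not being asked to complete forms. A missing *not* would explain it, but the documents do not confirm that.

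**Does the conflict disturb the sample size?** The plan states no confidence level or assumed proportion. Taking 95% and p = 0.5, the margin is 1.96 × √(0.25/n):

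- n = 270: 5.96 points (plan: 6)
- n = 200: 6.93 points (plan: 7)
- n = 100: 9.80 points (plan: 10)
- Enrollment: 270/(1 − 0.10) = 300 (plan: 300)

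All the plan's figures reproduce. If a share x of the 270 evaluable patients were lost and not replaced (x is an assumption), the margin would be:

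- x = 2%: n = 264.6, 6.02 points
- x = 5%: n = 256.5, 6.12 points
- x = 10%: n = 243, 6.29 points

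Precision hardly moves. Bias is a separate matter. If a share x of eligible patients is turned away, the percentage among those kept differs from that in all eligible patients by x × (percentage in those kept − percentage in those excluded). The bracket cannot exceed 100 points, so the bias is at most 2, 5 or 10 points for those values of x. These are outer limits, and the documents do not give x.

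**The case against.** Five points can fairly be made for the plan.

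1. **The footnote uses a different condition.** It speaks of inability to self-complete, while Section 5.3 speaks of inability to read. The protocol lists language and ability separately, so one could read the footnote as protecting only those who read the language but cannot fill in the form. That reading is possible and weakens this one limb. It leaves the clash with Section 5.2.2 untouched.
2. **The intended rule is not stated.** Adding a language criterion to Section 5.2.2 would also reconcile it with Section 5.3. It would, however, contradict the consecutive-enrollment rule, the claim to cover all Valchlor users, the synopsis and the SAP. Correcting Section 5.3 agrees with all of them.
3. **The number affected may be zero or very small.** This stands. Nothing shows that any center refused a patient on language.
4. **Spanish forms may not have existed.** The questionnaires in Appendices A and D are in English. This stands too, so the loss of Spanish readers' data is conditional.
5. **It is late.** Last patient first visit was planned for Q3 2017, the SAP is dated November 2019, and its Table 28 already shows counts with N=289. A wording change will probably not alter who was enrolled. This affects what the correction can achieve, not whether the text is wrong, and it is why disclosure belongs in the remedy.

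**Conclusion.** The concern holds. Section 5.3 as written bars patients whom every other eligibility statement admits, and the questionnaire language rule is inconsistent across four places. Both conflicts are in current, operative text.

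The size cannot be determined from the documents. The eligibility conflict reaches every patient who reads neither language at a center applying Section 5.3. The language conflict reaches the VAS, Skindex-29 and MF/SS-CTCL data of every Spanish-only reader at a center applying the Table 1 footnote or Section 5.9. The primary endpoint, BSA response, does not use questionnaires, so it is affected only through who was enrolled.

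The conclusion rests on reading the passages as they stand. Only the footnote limb needs the further assumption that inability to read a form implies inability to self-complete it. The point should be corrected because it touches the study's stated safeguard against selection bias and costs little to put right.

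**What to change.** - **Section 5.3:** insert *not* before *excluded*, so that patients who cannot read the questionnaire language are not asked to complete the forms and remain in the study. If the sponsor did intend a language exclusion, it must instead appear in Section 5.2.2 and the synopsis, and the statements about consecutive enrollment and covering all Valchlor users must be qualified in the protocol and the SAP.
- **Language rule:** state one rule, consistent with the questionnaire versions actually supplied to centers, in Section 5.3, the Table 1 footnote, Section 5.9 and the SAP Table 1 footnote.
- **Reporting:** state which rule centers applied, whether anyone was refused enrollment on language, and which language rule lies behind the denominators for the patient-reported endpoints.

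The cost is a protocol clarification, a correction to the SAP footnote and a query to the centers. No analysis changes.
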